#### 1.1.3 **Exploratory Studies:**

The primary goal of the exploratory studies is to identify potential predictive biomarkers of response as well as additional evidence of the mechanism of action of and resistance to ONC201. These will be performed in an exploratory fashion on select patients if there are adequate samples for analysis.

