longest diameter), be representative of all involved organs, but in addition should be those that lend themselves to reproducible repeated measurements. It may be the case that, on occasion, the largest lesion does not lend itself to reproducible measurement in which circumstance the next largest lesion which can be measured reproducibly should be selected. A sum of the diameters (longest for non-nodal lesions, short axis for nodal lesions) for all target lesions will be calculated and reported as the baseline sum diameters. If lymph nodes are to be included in the sum, then only the short axis is added into the sum. The baseline sum diameters will be used as reference to further characterize any objective tumor regression in the measurable dimension of the disease.

Non-target lesions. All other lesions (or sites of disease) including any measurable lesions over and above the 5 target lesions should be identified as **non-target lesions** and should also be recorded at baseline. Measurements of these lesions are not required, but the presence, absence, or in rare cases unequivocal progression of each should be noted throughout follow-up.

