### Cohort 2: Metastatic TNBC

Data which have been published suggest that a response rate (PR+CR) for treatment of recurrent or metastatic TNBC is approximately 30-35% (13-15). In order to establish the efficacy of this treatment in patients with metastatic TNBC, the primary objective in this cohort would be to determine if using ONC201 would rule out a 25% response rate and result in a response rate consistent with 45%. As such, this cohort will be evaluated using a single stage design in order to rule out an unacceptably low PR+CR rate of 25% ( $p_0=0.25$ ) in favor of an improved response rate of 45% ( $p_1=0.45$ ). Based on a one-sided exact binomial test, 29 patients would have 82% power to rule out 25% and result in findings consistent with a 45% PR + CR rate. At the end of the study, we would form the two-sided 80% and 95% CI about the observed percentages of both response (PR+CR) and clinical benefit (SD+PR+CR). 11 responses (PR+CR) in 29 patients (37.9%) has a two-sided 80% CI of 25.7-51.5%, which would be sufficiently interesting for further evaluation. As an early stopping rule, after 10 evaluable patients have been enrolled, if there are 0 or 1 with clinical benefit (SD+PR+CR), then the cohort would end accrual as soon as this would be determined since the 90% one-sided upper CI bound on 1/10 is 33.7%, which would be marginally too low for further interest. Both the PR+CR and SD+PR+CR rates can be formed at the interim time for descriptive purposes as well as for evaluation for early stopping. The study may need to pause accrual to evaluate if clinical benefit in the first 10 patients exceeds the early stopping rule.

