### Cohort 3: Advanced endometrial cancer

Published data from several trials report response rates of 8 to 15% for second line treatment in patients with advanced endometrial cancer (18-21). As such, it would be desirable if new treatments are associated with at least a 12-15% response rate for further consideration. In patients with advanced endometrial cancer, the primary objective of this study would be to determine if using ONC201 would rule out a 5% response rate and result in a response rate consistent with 25%. As such, the trial will be conducted using a single stage design (42) in order to rule out an unacceptably low PR+CR rate of 5% ( $p_0=0.05$ ) in favor of an improved response rate of 25% ( $p_1=0.25$ ). Based on a one-sided exact binomial test, 25 patients would have 90% power to rule out 5% and result in findings consistent with a 25% PR + CR rate. At the end of the study, we would form the two-sided 80% and 95% CI about the observed percentages of both response (PR+CR) and clinical benefit (SD+PR+CR). 3 responses (PR + CR) in 25 patients (12.0%) has a two-sided 80% CI of 4.5-24.8%, which is potentially worthy of further consideration, while 4 responses in 25 (16.0%) has a two-sided 80% CI of 7.2-29.5%, which would be sufficiently interesting for further evaluation. As an early stopping rule, after 13 evaluable patients have been enrolled, if there are 0 patients with clinical benefit (SD+PR+CR), then the cohort would end accrual since the 90% one-sided upper CI bound on 0/13 is 16.2%, which would be marginally too low for further interest. Both the PR+CR and SD+PR+CR rates can be formed at the interim time for descriptive purposes as well as for evaluation for early stopping. The study may need to pause accrual to evaluate if clinical benefit in the first 13 patients exceeds the early stopping rule.

Any secondary evaluations performed will be done in an exploratory fashion, with results presented without any formal adjustment for multiple comparisons.

*Abbreviated Title: ONC201 in advanced cancers*

*Version Date: 06/17/2020*

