#### **10.4.9 Exploratory Analyses**

Blood samples at baseline and Day 1 of each subsequent cycle, as well as biopsy specimens at baseline and cycle 2 will yield a set of biomarkers, such as markers of apoptosis, indications of mitochondrial damage and immune subsets. The difference of the values at cycle 1 vs. baseline and cycle 2 vs. baseline will be determined, and these differences will be used as a covariate for analysis of PFS in each cohort to see if the level of change in biomarkers may be associated with PFS. These analyses will be done in an exploratory fashion using Kaplan-Meier curves and log rank tests. The changes in the biomarkers will also be compared between responders and non-responders in the three cohorts using an exact form of a Wilcoxon rank sum test. All of these explorations will be done only if adequate patient data are available. Results will be presented without adjustment for multiple comparisons.

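### Section 10.4.9 links biomarker change to tumour response only by a responder/non-responder test, leaving the recorded change in tumour size unused and giving up a quarter to nearly all of the power

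*Combined protocol and SAP*

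**What the plan says.** Section 1.1.3 gives the main aim of the exploratory work as "to identify potential predictive biomarkers of response as well as additional evidence of the mechanism of action of and resistance to ONC201".

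Section 10.4.9 plans two analyses of biomarker change, taken as the differences of cycle 1 and of cycle 2 from baseline. The first relates the change to PFS by Kaplan-Meier curves and log rank tests. In the second, the changes are "compared between responders and non-responders in the three cohorts using an exact form of a Wilcoxon rank sum test". Both depend on there being enough patient data, and neither is adjusted for multiplicity. The section states no significance level, sidedness, power or minimum number of responders.

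Measurable disease is an entry requirement in all three cohorts (2.1.1.2, 2.2.1.1, 2.3.1.2), and imaging repeats every 8 weeks (3.4, 6.3). On the sum of target diameters, section 6.3.1 says: "The baseline sum diameters will be used as reference to further characterize any objective tumor regression in the measurable dimension of the disease". Section 6.3.3.1 then defines partial response as a fall of at least 30% in that sum. Nothing in 10.4.9 uses the percent change itself or the ordered categories CR, PR, SD and PD.

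**The concern.** RECIST needs the 30% cut in order to report a response rate. A biomarker correlation does not need it. Once the cut is made, a patient whose tumour shrank by 25% counts the same as one who progressed at the first scan. Section 1.2.3.2 reports that the phase I endometrial signal was stable disease in 3 of 5 patients, so this grouping could merge the outcomes that matter most for this drug.

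The test also depends on how many responders there are, and cohort 3 may have very few. At stake is the chance of seeing a real association between biomarker change and tumour shrinkage, which bears on the stated aim of the exploratory studies and on the use made of the mandatory paired biopsies.

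**Working it through.** **Inputs from section 10.2.** Cohort 3: "25 patients would have 90% power to rule out 5% and result in findings consistent with a 25% PR + CR rate", with 4 responses in 25 described as interesting. Cohort 2: "29 patients would have 82% power to rule out 25% and result in findings consistent with a 45% PR + CR rate".

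**The plan's own figures first.** Exact binomial:
- Cohort 3, success at 4 or more of 25: one-sided alpha 0.034, power 0.904 (plan: 90%). The 80% Clopper-Pearson intervals are 4.5-24.8% for 3/25 and 7.2-29.5% for 4/25, as printed.
- Cohort 2, success at 11 or more of 29: alpha 0.086, power 0.829 (plan: 82%).

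The design figures reproduce. The plan gives no power for 10.4.9.

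**Responders expected.**
- Cohort 3: 25 × 0.05 = 1.25 to 25 × 0.25 = 6.25.
- Cohort 2: 29 × 0.25 = 7.25 to 29 × 0.45 = 13.05.

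**A limit that needs no model.** With m responders among n patients and no ties, the smallest two-sided exact Wilcoxon p-value is 2 / C(n, m). For m = 1 and n = 25 this is 2/25 = 0.08. For m = 2 it is 2/300 = 0.0067. The probability of 0 or 1 responder in 25 is 0.277 + 0.365 = 0.642 at a 5% rate, 0.18 at 12% and 0.007 at 25%.

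**Power under assumptions.** The documents give no correlation or test level. Assume biomarker change and tumour-size change are bivariate normal with correlation 0.5, the test is two-sided at 0.05, and every evaluable patient has both values. Responders are those beyond the cut-point that gives the stated response rate. Simulation with 20,000 trials per setting:

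| Cohort | Response rate | Exact Wilcoxon | Spearman | Share of power lost |
|---|---|---|---|---|
| 3 (n=25) | 5% | 11% | 68% | 1 − 0.109/0.679 = 84% |
| 3 (n=25) | 12% | 27% | 68% | 1 − 0.266/0.679 = 61% |
| 3 (n=25) | 25% | 41% | 68% | 1 − 0.413/0.679 = 39% |
| 2 (n=29) | 25% | 48% | 76% | 1 − 0.482/0.757 = 36% |
| 2 (n=29) | 45% | 57% | 76% | 1 − 0.566/0.757 = 25% |

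Repeat simulations move these by a point or two. With the number of responders in cohort 3 held fixed at 1, 2, 3, 4, 5 and 6, Wilcoxon power is 0%, 19%, 27%, 33%, 35% and 39%.

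**Sensitivity to the correlation (cohort 3).** At 0.3, Spearman has 28% and Wilcoxon 5% to 17% over response rates of 5% to 25%. At 0.6, Spearman has 86% and Wilcoxon 16% to 58%.

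**Sensitivity to ties.** A percent-change analysis needs a rule for patients who progress through new or non-target lesions. Suppose 40% of 25 patients are tied as worst, with correlation 0.5. If they also have the worst target sums, Spearman power is about 62% to 64%. If their status is unrelated to target shrinkage among non-responders, it falls to about 16% to 38%, depending on the number of responders. With 4 responders it is about 28%, below the Wilcoxon test's 33%.

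Cohort 1 is not quantified, because the plan states no response rate for it.

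**The case against.** The strongest reply is that the planned test is valid, uses the same RECIST response as the primary endpoints of cohorts 2 and 3, and sits in an exploratory section that runs only when the data are adequate. One responder in 25 would hardly count as adequate, so the p-value floor of 0.08 may describe a test that is never run. It is also a failure only against a two-sided 0.05 level that the section does not set. A one-sided test could reach 1/25 = 0.04. Section 10.4.1 calls the analyses descriptive. The separate PFS analysis can distinguish durable stable disease from early progression without needing any responder.

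Much of this stands, and it limits how serious the point is. It does not remove the point. The adequacy condition has no stated minimum, and skipping the test would leave the biomarker-response question unanswered although the measurements exist. PFS is a different outcome, and a log rank test needs the biomarker change grouped at cut-points that 10.4.9 does not give.

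The objection that the gain rests on a favourable model is also sound. The tie results above show that the advantage can shrink to nothing.

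A reader might infer that the split throws away most of the power throughout. The figures do not support that. At correlation 0.5, half or more is lost with 1 to 4 responders. About 40% is lost at cohort 3's 25% target rate, and about 25% to 36% in cohort 2.

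**Conclusion.** The point holds as an efficiency weakness. Section 10.4.9 relates biomarker change to tumour response through a two-group split alone and leaves the recorded change in tumour size unused. Two results follow from the plan's own numbers: about 1 to 6 expected responders in cohort 3, and a 64% chance of 0 or 1 at a 5% response rate. The power comparison rests on an assumed correlation of 0.5, bivariate normality, two-sided 0.05 and complete pairs. On that basis the loss runs from about a quarter (cohort 2 at 45%) to nearly all (cohort 3 at 5%). Sections 1.1.3 and 5.1 restrict biomarker work to selected patients with adequate samples, so the real numbers may be smaller than those used here.

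It would be wrong to read this as a flaw in the trial's conclusions. No primary or secondary result, error rate or sample size depends on 10.4.9.

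**What to change.** Add to 10.4.9, for each cohort, a Spearman correlation between each planned biomarker change (keeping both differences from baseline) and the best percent change from baseline in the sum of target diameters. Include patients who have both biomarker values and a post-baseline tumour assessment. A patient who dies before cycle 2 has no cycle 2 difference and cannot enter that correlation.

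Rank patients whose best response is progression through new or non-target lesions as worst, and add a sensitivity analysis that uses their measured sums. Keep the exact Wilcoxon comparison and the PFS analysis alongside. State the rule before the data are examined.

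The cost is a few sentences, with no new samples, visits or patients. The downsides are that a ranking rule has to be chosen, and that the result describes tumour shrinkage rather than RECIST response.

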## 11 COLLABORATIVE AGREEMENTS

### 11.1 CLINICAL TRIAL AGREEMENT

The study agent, ONC201 is provided by Oncocoetics., Inc. under a Clinical Trial Agreement (NCI CTA #1035). Results or study data may be communicated to CTA partner, according to the terms of the NIH- Advanced Accelerator Applications SA CTA.

## 12 HUMAN SUBJECTS PROTECTIONS

### 12.1 RATIONALE FOR SUBJECT SELECTION

Subjects from all racial and ethnic groups are eligible for this trial if they meet the eligibility criteria. Efforts will be made to extend the accrual to a representative population. If differences in outcome that correlate to racial or ethnic identity are noted, accrual may be expanded or additional studies may be performed to investigate those differences more fully.

### 12.2 PARTICIPATION OF CHILDREN

The age group for enrollment on this trial is 18 or more years of age. Because no dosing or adverse event data are currently available on the use of ONC201 in participants < 18 years of age, children are excluded from this study.

### 12.3 PARTICIPATION OF SUBJECTS UNABLE TO GIVE CONSENT

Adults unable to give consent are excluded from enrolling in the protocol. However, re-consent may be necessary and there is a possibility, though unlikely, that subjects could become decisionally impaired. For this reason and because there is a prospect of direct benefit from research participation (section 12.5), all subjects will be offered the opportunity to fill in their wishes for research and care, and assign a substitute decision maker on the “NIH Advance Directive for Health Care and Medical Research Participation” form so that another person can make decisions about their medical care in the event that they become incapacitated or cognitively impaired during the course of the study. Note: The PI or AI will contact the NIH Ability to Consent Assessment Team (ACAT) for evaluation as needed for the following: an independent assessment of whether an individual has the capacity to provide consent; assistance in identifying and assessing an appropriate surrogate when indicated; and/or an assessment of the capacity to appoint a surrogate. For those subjects that become incapacitated and do not have pre-determined substitute decision maker, the procedures described in NIH HRPP SOP 14E for appointing a surrogate decision maker for adult subjects who are (a) decisionally impaired, and (b) who do not have a legal guardian or durable power of attorney, will be followed.

### 12.4 EVALUATION OF BENEFITS AND RISKS/DISCOMFORTS

ONC201 is an investigational agent for use in metastatic breast cancer and in advanced endometrial cancer. The protocol provides for detailed and careful monitoring of all patients to assess for toxicity. Toxicity data will be collected and reviewed to ensure that there were no severe toxicities that would preclude further patient enrollment. Patients will be treated with therapeutic intent and response to the therapy will be closely monitored.

*Abbreviated Title: ONC201 in advanced cancers*

*Version Date: 06/17/2020*

## 12.5 RISKS/BENEFITS ANALYSIS

### 12.5.1 Benefits

The potential benefit to a patient on this study is a reduction or stability in breast cancer or endometrial cancer, as well as potentially the prevention or delay in development of new metastatic lesions, which may or may not have favorable impact on symptoms and/or survival.

### 12.5.2 Risks

#### 12.5.2.1 Study Drug Risks

Risks include the possible occurrence of any of a range of side effects which are listed in the Consent Document or in section 13.1.2 of this protocol document. Frequent monitoring for adverse effects will help to minimize the risks associated with administration of the study agents.

#### 12.5.2.2 Radiation Risks

The study will involve radiation from the following sources:

- Up to 3 CT scans for the collection of biopsies
- Up to 8 CT scans per year for disease assessment
- 1 technetium-99 bone scan for disease assessment

Subjects may be exposed to approximately 11.59 rem. This amount is more than would be expected from everyday background radiation. Being exposed to excess radiation can increase the risk of cancer. The risk of getting cancer from the radiation exposure in this study is 1.2 out of 100 (1.2 %) and of getting a fatal cancer is 0.6 out of 100 (0.6%).

#### 12.5.2.3 Risks from Blood Draws:

Side effects of blood draws include pain and bruising, lightheadedness, and rarely, fainting.

#### 12.5.2.4 Risks of CT Scans:

In addition to the radiation risks discussed above, risks associated with CT scans are allergic reaction to and kidney damage from the contrast dye, nausea, vomiting, and anxiety.

#### 12.5.2.5 Risks of Technetium-99 Bone Scans:

In addition to the radiation risks described above, risks associated with technetium-99 bone scans are pain, bruising, injection site infection, and allergic reaction to the contrast agent.

#### 12.5.2.6 Specimen Collection Risks

Risks include those associated with specimen collection including pain, bleeding and the possibility of infection at the sampling site. All care will be taken to minimize risks that may be incurred by tumor sampling. However, there are procedure-related risks (such as bleeding, infection and visceral injury) that will be explained fully during informed consent. If patients suffer any physical injury as a result of the biopsy, immediate medical treatment is available at the NIH's Clinical Center in Bethesda, Maryland. Although no compensation is available, any injury will be fully

*Abbreviated Title: ONC201 in advanced cancers*  
*Version Date: 06/17/2020*

evaluated and treated in keeping with the benefits or care to which patients are entitled under applicable regulations.

### **12.5.3 Risks/Benefits Analysis**

The potential benefits from this therapy are stabilization or shrinkage of the tumor and a reduction in chances of developing new lesions, with decrease of symptoms caused by progressive disease. Given the efforts to minimize risk with the administration of this combination, this protocol involves greater than minimal risk, but presents the potential for direct benefit to individual subjects.

## **12.6 CONSENT PROCESS AND DOCUMENTATION**

The informed consent document will be provided to the participant or consent designee(s) (e.g., the legally authorized representative [LAR] if participant is an adult unable to consent) for review prior to consenting. A designated study investigator will carefully explain the procedures and tests involved in this study, and the associated risks, discomforts and benefits. In order to minimize potential coercion, as much time as is needed to review the document will be given, including an opportunity to discuss it with friends, family members and/or other advisors, and to ask questions of any designated study investigator. A signed informed consent document will be obtained prior to entry onto the study.

The initial consent process as well as re-consent, when required, may take place in person or remotely (e.g., via telephone or other NIH approved remote platforms) per discretion of the designated study investigator and with the agreement of the participant/consent designee(s). Whether in person or remote, the privacy of the subject will be maintained. Consenting investigators (and participant/consent designee, when in person) will be located in a private area (e.g., clinic consult room). When consent is conducted remotely, the participant/consent designee will be informed of the private nature of the discussion and will be encouraged to relocate to a more private setting if needed.

For the optional biopsy in the protocol, the patient will consent at the time of the procedure. If the patient refuses the optional biopsy at that time, the refusal will be documented in the medical record and in the research record.

### **12.6.1 Request for Waiver of Consent for Screening Activities**

Prior to the subject signing the consent for this study pre-screening activities listed in section [2.5.1](#) may be performed.

We request a waiver of consent for these activities as they involve only minimal risk to the subjects. A waiver will not adversely affect the rights and welfare of the subjects given that the activities are only intended to determine suitability for screening for participation in research protocols. These activities could not practicably be carried out without the waiver as central recruiting services, utilized in the NIH Clinical Center, perform pre-screening activities for multiple studies and obtaining consent for each one is beyond their resources. The subjects will be

**Abbreviated Title:** *ONC201 in advanced cancers*  
**Version Date:** *06/17/2020*

provided with additional pertinent information after participation as they will be informed whether or not they are eligible to sign a consent for additional screening.

### 13 PHARMACEUTICAL INFORMATION

#### 13.1 DRUG ONC201 (IND # 136939)

##### 13.1.1 Source

ONC201 is an investigational drug supplied under a Clinical Trials Agreement by Oncoceutics INC.

##### 13.1.2 Toxicity

Generally, ONC201 is well tolerated at all of the tested dose levels. To date, over 70 patients have taken at least one dose of ONC201 and no Grade IV events have been reported. One grade II allergic reaction occurred after the 5th dose of ONC201 625mg (q3 week schedule) that was managed by standard over the counter medications. One grade III neutropenia was transiently observed after the 5th dose of ONC201. The dose was reduced to 500mg q3weeks without recurrence of the neutropenia ([Table 6](#)).(2, 4)

Table 6: All Grade I AEs attributed (possibly related) to ONC201 on every 3-week dosing schedule for the Phase I trial.

ONC201 Dose	125mg	250mg	375mg	500mg	625mg
No. of Patients	1	1	1	1	24
Pyrexia	1	0	0	0	0
Fatigue	1	0	0	0	0
Elevated Amylase	0	0	0	0	2
Emesis	0	0	0	0	1
Nausea	0	0	0	0	1

\* Note: No drug-related AE > Grade 1 reported on the Phase I solid tumor trial

While human exposure to ONC201 is still somewhat limited at this time, side effects seen in animals included the following:

- Nausea
- Salivation
- Vomiting
- Abnormal breathing
- Twitching

**Abbreviated Title:** *ONC201 in advanced cancers*  
**Version Date:** 06/17/2020

- Abnormal walking or standing

While side effects are minimal, based on pharmacokinetic data, it would be reasonable to dose reduce if more significant side effects did occur. Based on the mean AUC and Cmax data from the phase I study, a dose reduction to 500mg weekly with two further reduction to 375mg weekly and then 250mg weekly would be reasonable and would likely not significantly affect clinical benefit (Figure 5).

[figure not shown]

Figure 5: Mean AUC and Cmax for each dose cohort following first dose of ONC201. *Image adapted from Stein et al, 2015 (2).*

The metabolism and excretion of ONC201 is still unknown at this time. However, it is suspected to be excreted by the kidneys. This is supported by preliminary observations in rats (unpublished data, communication with Oncoceutics, Inc).

The effects of ONC201 on the developing human fetus are unknown. For this reason, women of childbearing potential and men must agree to use adequate contraception (hormonal or barrier method of birth control; abstinence) prior to study entry and for the duration of study participation. Should a woman become pregnant or suspect she is pregnant while she or her partner is participating in this study, she should inform her treating physician immediately. An assessment should be made to ensure the potential benefit would justify a potential risk to the fetus.

It is not known whether ONC201 is excreted in breast milk. It is recommended that women do not breastfeed during treatment with ONC201 and for 2 months after the last dose.

[figure not shown]
**Abbreviated Title:** *ONC201 in advanced cancers*

**Version Date:** 06/17/2020

